### **List of Abbreviations**

CDC	Centers for Disease Control and Prevention
PI	Principal Investigator
WHO	World Health Organization

### Protocol Summary

Title:	Optimizing vaccine introduction
Population:	1,000 Parents of children or adolescents in Shanghai (objectives 1-3) 120 vaccination providers (objective 4)
Number of Sites:	40 immunization clinics Several elementary, middle, and high schools
Study Duration:	First wave (summer 2019): 3 months Second wave (summer 2022): 3 months
Study Design:	Experiment
Objectives:	
Primary Objective:	To determine how the framing of the HPV vaccination across several dimensions affects short-term willingness to receive it
Secondary Objective:	To determine how the framing of the HPV vaccination across several dimensions affects sustained willingness to receive it
Tertiary Objective:	To determine how the framing of the HPV vaccination across several dimensions affects actual uptake of vaccine
Quaternary Objective:	To understand what factors providers think are important when promoting the HPV vaccine

## 2 Background Information and Scientific Rationale

### 2.1 Background Information

Since 2000, the US has licensed ten new vaccines (Plotkin & Plotkin, 2013), but research on vaccine hesitancy has not kept pace with vaccine development. HPV's faltering rollout in the US is a cautionary tale about how not to inform the public about a vaccine. Prior to vaccine introduction, awareness of HPV was low (Friedman & Shepeard, 2007). The Advisory Committee on Immunization Practices (ACIP) published its first set of recommendations in 2006 (Markowitz et al., 2007, 2014); early reports focused on the relation between vaccination and sexual intercourse (Clark, 2007b, 2007a). The vaccine was not recommended for routine use in males until 2011. Parents have remained concerned about the HPV vaccine's impact on their child's sexual behaviors (Brewer & Fazekas, 2007), and uptake remains low—37% for girls and 13% for boys in 2014 (Lancet, 2016). Programs that have attempted to promote HPV vaccination since its introduction in the US have met with mixed success (Walling et al., 2016). In contrast, the hepatitis B vaccine—which protects against an infection largely spread through injection drug use or sexual intercourse—has not had such a pushback from the public, likely because it was marketed as vaccine that protects against the development of chronic infection in young infants (Hardt et al., 2016). The scientific premise of this study is that the period when a vaccine is adopted into the national immunization program is the critical window for shaping public discourse about and uptake of the vaccine. As more vaccines are formulated, it is critical that we determine how to best promote these vaccines to the public.

### 2.2 Scientific Rationale

This grant proposal will be carried out in China so I can focus on changes in attitudes toward vaccines as new vaccines are added to the national immunization schedule. I will focus on HPV—a sexually transmitted disease that causes cancer. Only 14.5% of Chinese have heard of HPV (Li et al., 2009). This proposal represents a substantial contribution to the field by evaluating the best methods for introducing a new vaccine to market. These findings can help increase vaccine uptake and prevent disease.

### 2.3 Potential Risks and Benefits

The main risk associated with this study would be loss of confidentiality – where someone would be able to identify participants and discover how they responded.

Participants will not directly benefit from study, although others might benefit. This is because we may be able to improve vaccination coverage rates in the future with our findings about what characteristics about vaccines are or are not important to emphasize.

### 3 Objectives

**Primary Objective**

To determine how the framing of the HPV vaccination across several dimensions affects short-term willingness to receive it

**Primary Outcome Measures**

At the end of the survey, parents will respond to a series of statements about their willingness to get their child vaccinated (which will be assessed on a 5-point scale from “strongly willing” to “not at all willing”). In the analysis, this outcome can be analyzed either as a continuous/ordinal outcome or as a dichotomized outcome (agree vs disagree).

**Secondary Objective**

To determine how the framing of the HPV vaccination across several dimensions affects sustained willingness to receive it

**Secondary Outcome Measures**

Same as primary outcome measure (but asked 3 years after initial intervention).

**Tertiary Objective**

To determine how the framing of the HPV vaccination across several dimensions affects actual uptake of vaccine

**Tertiary Outcome Measures**

Uptake of HPV vaccination, as recorded in the electronic immunization registry (four years after initial intervention).

**Quaternary Objective**

To understand what factors providers think are important when promoting the HPV vaccine

**Quaternary Outcome Measures**

We will enroll vaccination providers from all clinics to complete a simple questionnaire about HPV vaccination.

## 4 Study Design

Participants will be randomized into two groups to receive information about the HPV vaccine. This information will be depicted on a sheet of paper using graphs and words. For one group, they will receive information similar to how it was historically presented in the US (as a sexually transmitted disease). The other group will receive modified messaging that downplays both the “gendered” nature of the disease and the role of sexual transmission and emphasizes that HPV is a cancer. The exact messaging will be developed in consultation with a mentor, [name], and after taking related coursework (as part of training goal 1). Although I believe this latter method will result in higher acceptance of HPV, the former method of presenting the information is still ethical because it will replicate materials from the WHO (World Health Organization, 2014). We will also collect demographic and socioeconomic data, along with measures of exposure to various information sources, including traditional media, social media, and messaging from hospitals and doctors.

Parents will provide information at three different stages. For wave 1 (this protocol), they will spend 30 minutes at a clinic filling out a paper questionnaire. For wave 2 (a separate protocol to be developed in the future), they will be re-contacted by phone and asked if they want to come to the clinic again to participate in another study. The third stage of data collection involves us linking their questionnaire data to their child’s vaccination records; we notify them about this in the informed consent document, but since we will also collect their child’s vaccination record number at the time of wave 1, we will not need to recontact them in the future in order to access the electronic immunization registry.

## 5 Study Population

### 5.1 Selection of the Study Population

Participants may be sampled from several locations. There is a two-stage selection procedure. Townships have already been sampled (through a random selection procedure, stratified by district within the city) based on the population of their surrounding township according to the 2010 Census.

The primary location would be immunization clinics. Parents could be selected as a convenience sample (from parents already at the clinic for vaccination appointments), or they could be sampled randomly from population registers at the clinic.

For the first wave of data collection, a convenience sample within each clinic will be taken of parents of children. On days of data collection, we (i.e., the PI or a master's student) will go to the clinic in the morning and explain the study. As the vaccine providers vaccinate children throughout the day, they will direct parents of children into a private room, where we can explain the study more, ask for informed consent, and give the parent-participant a questionnaire.

Another potential study location will be middle schools or high schools in Shanghai. We will attempt to go to schools within the townships that we have already selected, but the extent to which we use schools will be dependent on their availability. At schools, teachers will send questionnaires and informed consent forms to students, and students will bring these documents home to their parents to fill out.

We will enroll 120 vaccination providers from all clinics (an average of 3 per clinic) to complete a simple questionnaire about HPV vaccination.

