#### **Monitoring procedures**

[name] assures that informed consent is obtained prior to performing any research procedures, that all subjects meet eligibility criteria, and that the study is conducted according to the IRB-approved research plan. The research protocol will be reviewed by the University of Michigan IRB and the Shanghai CDC ethical review committee (collectively referred to as the “IRBs”).

Study data are accessible at all times for the PI and mentors to review. The PI and mentors will review study protocol prior to each period of data collection, and will review study conduct, drop-outs, and protocol deviations one month and two months after the beginning of each data collection period. The PI will review AEs and SAEs individually in real-time and aggregate on a weekly bases (see the “AE Management” and “Data analysis plans” sections below). The PI ensures all protocol deviations, AEs, and SAEs are reported to the NIH and IRBs according to the applicable regulatory requirements.

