## 9 Informed Consent Process

Many parents and children visit vaccination clinics every day in China to receive mandatory vaccines. They wait in line until they are called to visit with a nurse (“vaccination provider”), who discusses vaccination options with them, and then directs them to another nurse who will obtain the vaccines they need and administer the dose(s) required. Afterward, the parents and children are supposed to wait at clinics for 30 minutes after vaccination to see if there is any adverse reaction to the vaccine. A large age range of children come into the clinic, and so we will notify the vaccination providers what are required age range is (2-18 years), and parents of those children will then be told by the nurses about our study. The nurses will mention to parents whose children fall into the age category (2-18 years) that a study is taking place about their attitudes towards vaccination. Vaccination providers will then direct parents to come into a private room to learn more about the study. Of course, some parents may be uninterested at this point and we would never see them. At the end of our time at each clinic, we will ask the nurses how many parents did not come and see us (so we can tally up our response rate).

Clinics have a few private rooms for conducting meetings which are out of the way from where other parents are waiting (before and after vaccinations). Within such a room we will ask parents the screening question (is their child between 2-18 years), and if they answer affirmatively, give the parents the informed consent form and ask if they want to voluntarily participate in this study. We will give them time to read through the document and sign and ask any questions to study staff.

Similarly, for parents sampled at schools, the forms (questionnaire, enrollment log, and informed consent form) will be sent by the teacher to the child’s home. The teacher will be responsible for collecting these documents and handing them back to the study team.

If they sign the informed consent, we will file it in a separate location from the questionnaires. This questionnaire is something that the parents can fill out themselves, and study staff will be available to answer any questions.

Any follow-up survey (i.e., 3 years later) will involve the parents being re-consented.

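### At schools the consent form and questionnaire go home in one unsupervised packet, so a parent can see the assigned message before consenting, and unreturned packets are not counted by arm

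*Combined protocol and SAP*

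**What the plan says.** **Schools.** Section 5.1 allows schools as a further recruitment site, subject to availability, and the Protocol Summary lists them among the sites. There, "teachers will send questionnaires and informed consent forms to students, and students will bring these documents home to their parents". Section 9 adds that "the forms (questionnaire, enrollment log, and informed consent form) will be sent by the teacher to the child’s home", and then: "The teacher will be responsible for collecting these documents and handing them back to the study team". No step holds anything back until consent is signed.

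**Clinics.** The order is staged and staff are present. Parents go to a private room "where we can explain the study more, ask for informed consent, and give the parent-participant a questionnaire". Section 9 puts the screening question before the consent form.

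**Consent rule.** Under Monitoring procedures (Section 6.1), a named member of the team "assures that informed consent is obtained prior to performing any research procedures".

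**Intervention and outcome.** Section 4: "Participants will be randomized into two groups to receive information about the HPV vaccine". The information is on a paper sheet. Section 7.1 measures willingness at the end of the survey. The child's vaccination record number, needed for the registry outcome, is collected at wave 1 (Section 4).

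**Statements that point to clinics only.** Section 4 has wave 1 parents completing the questionnaire at a clinic, Section 6.2 (AE Management) places all study procedures at an immunization clinic, and Section 7.2 places parent enrolment in immunization clinics.

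**The concern.** Randomisation protects the comparison only if the decision to take part is made before the parent sees the assigned message, or if everyone randomised is followed whatever they decide. The clinic route can meet the first condition. The school route, as written, secures neither.

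The two messages are expected to differ in how well they are received; Section 4 predicts higher acceptance for the modified one. A school parent who can read the message and then decide whether to send the packet back may decide partly because of it. The returned questionnaires would then be a set selected after exposure, and regression among returners (Section 7.4) does not repair that. A non-returner also supplies no record number, so the same selection passes to the registry uptake outcome.

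The plan could not detect this afterwards. The response tally in Section 9 asks clinic nurses about parents who did not come forward. The review of drop-outs in Section 6.1 is not described as being by arm or as covering unreturned school packets.

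**Working it through.** **Step 1. Does the message reach school parents before consent?** The packet list in Section 9 has three items: questionnaire, enrollment log and consent form. The message sheet is not one of them. But the message is on paper (Section 4), the primary outcome comes at the end of the questionnaire (Section 7.1), and no other delivery route is described. For a school parent to contribute to the primary objective, the sheet must come with or inside the packet. This is an inference. The plan does not say when or by whom school parents are randomised.

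**Step 2. The plan's own figure.** Section 7.2 powers for 70% v 80%. Alpha, power and allocation ratio are not stated. With two-sided 5%, 80% power, 1:1 allocation and the pooled formula:

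n per arm = [1.96·√(2·0.75·0.25) + 0.8416·√(0.7·0.3 + 0.8·0.2)]² / 0.10² = 293.2, rounded up to 294, so 588 in total. Then 588 × 1.69 = 993.7, or 994.

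Both stated figures reproduce, and this point does not dispute them. They set the scale: the trial looks for 10 points.

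**Step 3. Effect of selective return, school parents only.** Let p be true willingness in an arm, and rw and ru the return rates of willing and unwilling parents. Willingness among returners is

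p·rw / (p·rw + (1 − p)·ru).

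The return rates are assumptions; the documents give none. For rw = 60% and ru = 50%:
- 70% arm: 0.42 / (0.42 + 0.15) = 73.7%
- 80% arm: 0.48 / (0.48 + 0.10) = 82.8%

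| Return, willing v unwilling | 70% arm observed | 80% arm observed, same pattern | Difference, pattern in 70% arm only | Difference, pattern in both arms |
|---|---|---|---|---|
| 80% v 70% | 72.7% | 82.1% | 7.3 | 9.3 |
| 60% v 50% | 73.7% | 82.8% | 6.3 | 9.1 |
| 60% v 40% | 77.8% | 85.7% | 2.2 | 7.9 |

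The fourth column subtracts from an undistorted 80%. Most of the shrinkage comes from assuming that return depends on willingness in one arm only.

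**Step 4. Dilution over the whole trial.** The school share is not stated. The 3.7-point loss in the 60% v 50% one-arm case (10 − 6.3) becomes about 0.4 points if schools supply 10% of parents, 0.9 at 25% and 1.8 at 50%.

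**Step 5. No true effect.** Take 70% willing in both arms. In one arm all parents return at 80%; in the other, willing parents return at 80% and unwilling at 60%. The spurious difference among school parents is 0.56 / (0.56 + 0.18) − 0.70 = 5.7 points. With 1,000 parents and design effect 1.69, the effective number per arm is 1,000 / 1.69 / 2 = 295.9 and the standard error is √(2·0.7·0.3 / 295.9) = 3.77 points.

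| School share | Bias, points | Rejection rate of a nominal 5% test |
|---|---|---|
| 10% | 0.6 | 5.3% |
| 25% | 1.4 | 6.6% |
| 50% | 2.8 | 11.7% |
| 100% | 5.7 | 32.5% |

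**The case against.** The best defence is that the school route is marginal and thinly described. Schools are optional, clinics are the primary location, and Sections 4, 6.2 and 7.2 read as if parents are enrolled and studied only in clinics. On that reading the problem never arises. This limits the size of the problem but does not settle it: Sections 5.1 and 9 and the Protocol Summary still provide for schools, so the plan conflicts with itself.

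A reader might infer that the school procedure contradicts the consent-first rule. The documents do not show that. The order inside the packet is not stated, and a parent may sign before reading further. What stands is that nothing in the procedure secures the rule.

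A reader might also infer that the parents who remain in the sexual-transmission arm must be the more willing ones, so that the difference is understated. No passage gives return rates or links return to framing. The bias could go either way, and there is none if return does not depend on arm and willingness together.

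Finally, it is fair to say that asking for consent first does not remove bias in the primary outcome, because a consented parent can still read the message and not return the questionnaire. That stands. The gain is a known randomised denominator, a secured consent order and a protected registry outcome.

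**Conclusion.** The concern holds as a gap in procedure. As written, a school parent can see the assigned message before consenting, return may depend on arm and willingness together, unreturned packets are not counted by arm, and non-returners have no record number for the registry outcome. The consent-first rule in Section 6.1 is not secured for this route.

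The conclusion rests on the inference that the message travels with or inside the packet, and on schools being used at all. The size and direction of any bias are unknown. Under the assumed 60% v 50% return, a true 10-point difference among school parents appears as 6.3 points if the pattern is confined to one arm and 9.1 if it is common to both. These figures must not be read as the whole-trial effect, which scales with the unstated school share and is small if few school parents enrol. The sample size is unaffected.

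**What to change.** 1. Reconcile Sections 5.1 and 9 with Sections 4, 6.2 and 7.2. Confining parent enrolment to clinics would remove the issue, at the price of the school parents.
2. If schools are used, stage the packet. Send the consent form, screening question and a request for the child's record number first. Randomise when these come back signed and complete. Then release the message sheet and questionnaire in a sealed, numbered envelope.
3. Log envelopes sent and returned by arm.
4. Keep every consented and randomised parent in the registry uptake analysis, whether or not the questionnaire is returned.
5. Report the primary comparison with and without school parents. Report non-return after consent by arm, with a sensitivity analysis that varies the assumed willingness of non-returners separately in each arm.

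The cost is one extra round trip through the teacher, a short amendment, somewhat slower school recruitment and possibly a few more drop-outs between the two steps, which would now be countable by arm. The clinic route and the sample size do not change.

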### 5.2 Inclusion and Exclusion Criteria

Participants can be included if they are parents of children 2-18 years old.

All vaccination providers at a clinic which offers an HPV vaccine are eligible.

## 6 Data and Safety Monitoring Plan

### 6.1 Study Procedures

#### **Oversight responsibilities**

Oversight of the trial is provided by the Principal Investigator (PI), [name] and his mentors on the study: Drs. [name], [name], and [name].

#### **Monitoring procedures**

[name] assures that informed consent is obtained prior to performing any research procedures, that all subjects meet eligibility criteria, and that the study is conducted according to the IRB-approved research plan. The research protocol will be reviewed by the University of Michigan IRB and the Shanghai CDC ethical review committee (collectively referred to as the “IRBs”).

Study data are accessible at all times for the PI and mentors to review. The PI and mentors will review study protocol prior to each period of data collection, and will review study conduct, drop-outs, and protocol deviations one month and two months after the beginning of each data collection period. The PI will review AEs and SAEs individually in real-time and aggregate on a weekly bases (see the “AE Management” and “Data analysis plans” sections below). The PI ensures all protocol deviations, AEs, and SAEs are reported to the NIH and IRBs according to the applicable regulatory requirements.

### 6.2 Expected Adverse Events

#### **Expected AEs**

Because we are not testing any therapy, are not taking any biological samples, and are only engaging in an educational/behavioral intervention, we do not expect any “physical” AE to occur. However, we potentially could change someone’s attitude about the HPV vaccine for the worse. Because our goal in this study is to identify ways in which we can improve acceptance of HPV vaccination, if it turns out that we are in fact making people more vaccine hesitant, that would be a behavioral/attitudinal AE.

Although no previous study in China has replicated exactly what we will plan to do, observational studies have found a variation in acceptability of HPV vaccine. One study in Hong Kong found “the prevalence of parental acceptability of HPV vaccination for the index son and daughter were: [...] 51.6% and 63.0% (free vaccination)” (Wang et al., 2018). Another study from Jinan found that “female students were more willing to take the HPV vaccine than male students (76.7% vs 58.6%)” (Xue et al., 2017).

If, from preliminary analyses (see below), we find that acceptability of the vaccine is less than 40% (about 10% to 20% less than acceptability of what was found in previous studies – we are using a lower number to account for variability in the study population characteristics), we will stop data collection (enrollment of new participants), notify the IRBs, and identify ways to change the protocol prior to re-starting data collection.

